GlaxoSmithKline group of companies WWEpi Project number: PRJ2678/205881

TITLE PAGE

Division: Worldwide Development

Information Type: Worldwide Epidemiology Study Protocol

Title: Evaluation of referring HCPs' and parents'/carers'

understanding of specific risks associated with StrimvelisTM

treatment

Compound Number:

GSK2696273

Development Phase IV

Effective Date:

24-MAR-2017

Subject:

Rare Diseases; Strimvelis; Adenosine Deaminase Severe

Combined Immunodeficiency; (ADA-SCID); Safety and

Effectiveness of Risk Minimisation Activities; Post Authorisation

Safety Study (PASS) Category 3

Author(s):

PPD

Copyright 2017 the GlaxoSmithKline group of companies. All rights reserved. Unauthorised copying or use of this information is prohibited

PASS Information *

Title	Evaluation of referring HCPs' and parents'/carers' understanding of specific risks				
	associated with Strimvelis™ treatment				
Protocol version identifier	Draft 1				
Date of last version of protocol 6 th December 2016					
EU PAS (ENCEPP) register number	[Registration number in the EU PAS register; indicate "Study not registered" if the study has not been registered in the EU PAS (ENCEPP) register. Note: all non-interventional PASS should be entered in the EU-PAS register before study start as per SOP_72635.] <will be="" entered="" finalized="" is="" once="" protocol="" the=""></will>				
Active substance	Autologous CD34+ enriched cell fraction that contains CD34+ cells transduced with retroviral vector that encodes for the human ADA cDNA sequence. (ACT Code available after marketing authorisation)				
Medicinal product	Strimvelis TM				
Product reference	Not yet available				
Procedure number	EMEA/H/C/003854				
Marketing authorization holder(s)	GlaxoSmithKline Trading Services Limited [name] Ireland				
Joint PASS	No				
Research question and objectives	To evaluate the effectiveness of routine and additional risk minimization measures by assessing the understanding of parents/carers and referring HCPs with regard to specific risks associated with Strimvelis.				

2017N320222_00 GlaxoSmithKline group of companies

WWEpi Project number: PRJ2678/205881

Country(-ies) of study	Italy and other European Union (EU) member states, and other non EU countries to be determined as patients are treated.	
Author	[name] Center, [name].	GSK Medicine od Road,

MARKETING AUTHORISATION HOLDER(S) *

1. LIST OF ABBREVIATIONS

ADA	Adenosine deaminase
ADA-SCID	Adenosine deaminase severe
	combined immunodeficiency
AE	Adverse event
BMT	Bone marrow translpant
CD34+	Hematopoetic progenitor stem
	cells
CRO	Contract research organization
dAXP	Deoxyadenosine nucleotides
DNA	Deoxyribonucleic acid
ENCePP	European Network of Centres
	for Pharmacoepidemiology and
	Pharmacovigilance
ERT	Enzyme replacement therapy
EU	European Union
EU RMP	European Risk Management
	Plan
GTRC	Gene Therapy Registry Centre
GSK	GlaxoSmithKline
НСР	Healthcare provider
HLA	Human leukocyte antigen
HSCT	Hematopoetic stem cell
	transplant
HSR	Hospital San Raffaele, Italy
KRM	Key Risk Message
MUD	Matched unrelated donor
NK	Natural killer cells
PASS	Post-Authorization Safety
	Study
PEG-ADA	Polyethylene glycol modified
	bovine adenosine deaminase
PVP	Pharmacovigilance Plan
RBC	Red blood cell
SAE	Serious adverse event
SCID	Severe combined
	immunodeficiency
SmPC/PIL	Summary of Product
	Characteristics/Patient
	Information Leaflet
US	United States
WBC	White blood cell

WWEpi Project number: PRJ2678/205881

Trademark Information

Trademarks of the GlaxoSmithKline group of companies

STRIMVELISTM

Trademarks not owned by the GlaxoSmithKline group of companies

None

3. ABSTRACT

Title: Evaluation of referring HCPs' and parent/carers' understanding of specific risks associated with StrimvelisTM treatment

Rationale and background: Adenosine deaminase (ADA) deficiency results in severe combined immunodeficiency (SCID), a fatal autosomal recessive inherited immune disorder. Strimvelis is a medicinal product developed by GlaxoSmithKline (GSK) that restores ADA function in hematopoietic cell lineages, thereby preventing the pathology caused by purine metabolites (i.e., impaired immune function). Strimvelis is indicated for the treatment of patients with ADA-SCID, for whom no suitable human leukocyte antigen (HLA)-matched related stem cell donor is available.

Research question and Objective(s): The objective of this study is to evaluate the effectiveness of routine and additional risk minimization measures (*e.g.* Summary of Product Characteristics/Patient Information Leaflet (SmPC/PIL), educational materials) by assessing the understanding of referring HCPs and parents/carers with regard to the specific risks associated with Strimvelis.

Study Design: In this cross-sectional study, surveys will be provided to referring HCPs and parents/carers of children approximately six months after treatment with Strimvelis. Both surveys were developed to assess the understanding of the risks associated with Strimvelis treatment. The outcome of the surveys is the proportion of referring HCPs and parents/carers' that provide correct responses to a series of questions concerning the specific risks associated with Strimvelis. Additional analyses will assess implementation metrics (e.g., proportion of respondents who received the educational materials).

Population: A non-interventional registry is being implemented to prospectively monitor the long-term safety and effectiveness of Strimvelis. Referring HCPs and parents/carers of patients enrolled within the registry will be contacted and asked to participate in this study.

Variables: Two survey instruments with approximately 20 questions are included in this study, a HCP survey and a parent/carer survey. Survey questions are based on the Strimvelis prescribing information and educational materials, and will evaluate HCPs' and parent/carers' understanding of the key risk messages (KRMs). The questions will also assess HCPs' and parent/carers' awareness, receipt, and reading of the educational materials. Demographic information, including geographic region and HCP specialty, will be collected.

Data sources: Referring HCPs and parents/carers of patients enrolled within the registry will be asked to complete the survey. Surveys will be developed in English and translated in the parent/carers' and HCPs' local language. Survey's will be conducted via telephone interview.

Study size: The study will recruit for approximately two years until 10 referring HCPs and 10 parents/carers have completed their respective surveys (length of study may vary contingent upon product uptake). Results of surveys are distinct for each of the groups and will be reported separately.

Data analysis: Data from all survey respondents will be analysed and reported as descriptive statistics. A frequency distribution of responses to each question will be presented. Summary statistics will be prepared describing the proportion of referring HCPs and parents/carers for whom questionnaires were returned relative to the total number of referring HCPs and parents/carers of patients eligible for enrolment into the study.

4. AMENDMENTS AND UPDATES

None

5. MILESTONES

Milestone	Planned date
Start of data collection	Q2 2017
End of data collection	Q3 2020
Final report of study results	Q1 2021

6. RATIONALE AND BACKGROUND

6.1. Background

ADA deficiency results in severe combined immunodeficiency (SCID), a fatal autosomal recessive inherited immune disorder. ADA deficiency is extremely rare, with an overall prevalence ranging from 0.22 to 0.68 per 100,000 live births, or fewer than 50 children per year in the United States (US) and European Union (EU) combined.

ADA is a ubiquitous enzyme of purine metabolism, and mutations in the ADA gene lead to accumulation of deoxyadenosine nucleotides (dAXP) in plasma, white blood cells, (WBCs), red blood cells (RBCs), and tissues. The main features of ADA-SCID are profound lymphopenia; impaired differentiation and function of T cells, B cells, and natural killer (NK) cells; recurrent infections; and failure to thrive [Hirschorn, 1999; Chapel, 2003]. Non-immunological abnormalities may also occur as a consequence of the systemic metabolic defect and include hepatic, lung, and skeletal alterations, as well as neurological deficits affecting motor function, hearing, and cognitive/behavioral deficits [Hirschorn, 1999; Gaspar, 2010; Sauer, 2009]. Moreover, it is now apparent that the clinical spectrum extends into a late-onset ADA deficiency diagnosed between 3 and 15 years of age, in which there is significant immunodeficiency as well as other associated findings, including elevated IgE, eosinophilia, immune dysregulation manifested by autoimmunity including autoimmune hypothyroidism, diabetes mellitus, hemolytic anemia, and idiopathic thrombocytopenia [Hirschorn, 2014]. As a result of recurrent infections, patients with ADA-SCID often present initially to a family physician or general pediatrician before care is eventually transferred to a pediatric immunologist, who may ultimately make the diagnosis and consider treatment options.

Patients with ADA-SCID can be effectively treated with conventional bone marrow transplant (BMT) (also referred to as hematopoietic stem cell transplant [HSCT]) from allogeneic donors, but the better outcomes for this intervention are only achieved when an HLA-matched family donor is available. Unfortunately, such a donor is a viable

WWEpi Project number: PRJ2678/205881

option for fewer than 25% of patients with ADA-SCID [Hirschorn, 2014]. Stem cells from HLA-matched siblings or family members are usually given without chemotherapeutic conditioning to reduce the risk of chemotherapy-associated toxicity.

In those ADA-SCID patients for whom related matched donors are not available, alternative sources of stem cells are used for transplantation. These procedures may require chemotherapeutic preconditioning and are associated with increased morbidity and mortality primarily related to inadequate immune reconstitution and graft versus host disease. Decreased long-term survival (compared with matched sibling or matched family donor) has been observed with less well-matched donor sources of stem cells. Specifically, long-term survival rates (after a median follow-up of 6.5 years) were significantly better with matched sibling and family donors at 86% and 81%, in comparison with 67%, 43%, and 29% after HCT from matched unrelated donors (MUDs), haplo-identical donors, and mismatched unrelated donors, respectively [Gaspar, 2010; Hassan, 2012]. Survival data by decade has also been studied, to evaluate whether transplantation outcome had improved over time as a result of increased awareness of SCID, greater experience of transplantation in these children, and improvement in transplant-related processes/medications. Overall survival improved by decade for all donor types, from 51.7% pre-1991 to 72.5% from 2000-2009. In the subgroup of haploidentical transplant recipients, overall survival improved from 40% (8/20) pre-1991 to 71.4% (5/7) from 2000-2009. In this latter period, haploidentical transplant was successful in 42.3% of patients (3/7), as two transplants did not engraft [Hassan, 2012].

Strimvelis (or GSK2696273, its investigational name) is a gene therapy that aims to restore ADA function in hematopoietic cell lineages and prevent the immunological manifestations caused by purine metabolites (i.e., impaired immune function). Strimvelisis a CD34+ cell enriched dispersion of human autologous bone marrow-derived hematopoietic stem/progenitor cells for infusion that have been transduced with a retroviral vector containing the human adenosine deaminase (ADA) gene. The cell populations that constitute the active substance are genetically modified CD34+ cells and unmodified CD34+ cells. Cells that have been genetically modified will contain one or more copies of the human ADA transgene. The treatment regimen consists of autologous bone marrow harvested for gene transduction, non-myeloablative pre-conditioning with the chemotherapy agent busulfan, followed by gene therapy with Strimvelis (infusion of gene modified CD34+ cells).

Strimvelis is currently administered at Hospital San Raffaele (HSR) in Italy by physicians with previous experience in the treatment and management of patients with ADA-SCID and the use of autologous CD34+ *ex vivo* gene therapy products. Prior to treatment with Strimvelis, patients must be tested and shown to be negative for the presence of infectious agents as listed in the current EU Cell and Tissue Directive. The patient must be able to donate adequate CD34+ cells in order to deliver the minimum of 4 million purified CD34+ cells/kg required for the manufacture of Strimvelis. The recommended dose range of Strimvelis is between 2 and 20 million CD34+ cells/kg and is intended to be administered as an intravenous infusion once only.

6.2. Rationale

Strimvelis is only to be used in the ultra-rare disorder ADA-SCID and in patients for whom no suitable human leukocyte antigen (HLA)-matched related stem cell donor is available. Routine risk minimization activities to mitigate risks are communicated via labelling (e.g. SmPC/PIL). GSK also provides additional risk minimization measures that take into account guidelines on safety and efficacy follow-up of advanced therapy medicinal products (ATMPs), the product risk profile, and the very restricted scope of the administration procedure (e.g. treatment for patients who do not have an adequeate HLA matched related donor for HSCT) to facilitate informed decision making and to support risk minimization when initiating treatment. These additional risk minimization measures, including educational materials, will be distributed to parents/carers and referring HCPs. The educational materials specifically address the following safety concerns: autoimmunity, unsuccessful response to gene therapy, malignancy due to insertional oncogenesis (e.g. leukaemia, myelodysplasia) and pregnancy.

7. RESEARCH QUESTION AND OBJECTIVE(S)

The objective of this study is to evaluate the effectiveness of routine and additional risk minimization measures (*e.g.* SmPC/PIL, educational materials) by assessing the understanding of parents/carers and referring HCPs with regard to the following:

Safety concerns:

- Malignancy due to insertional oncogenesis (e.g. leukaemia, myelodysplasia)
- Autoimmunity
- Unsuccessful response to gene therapy
- Pregnancy

Other areas of interest:

- Requirement for long-term monitoring
- Patient alert card

This study will help determine whether the current routine and additional risk minimisation measures have been successfully implemented. The study will assess the proportion of parents/carers and referring HCPs providing correct responses to a series of questions concerning specific risks associated with Strimvelis. Additional analyses will assess implementation metrics (e.g. proportion of respondents who received the educational materials).

8. RESEARCH METHODS

8.1. Study Design

This is a cross-sectional study in which surveys will be conducted in EU and non-EU countries and provided to both parents/carers and referring HCPs of children approximately six months after treatment with Strimvelis. The two surveys will be developed to evaluate the effectiveness of routine and additional risk minimization measures (*e.g.* SmPC/PIL, educational materials) by assessing the understanding of referring HCPs and parents/carers with regard to the specific risks associated with Strimvelis. All data collected during the surveys will be confidential and anonymzed to protect the identity and privacy of the survey participants.

8.2. Study Population and Setting

Strimvelis is indicated for the treatment of patients with ADA-SCID, for whom no suitable human leukocyte antigen (HLA)-matched related stem cell donor is available. A registry study (PRJ2684/200195) will be implemented with long-term prospective, non-interventional follow-up of the safety and effectiveness of Strimvelis. Patients in the registry will be monitored for at least 15 years post-treatment with Strimvelis.

Parents/carers and referring HCPs of patients enrolled within this registry will be contacted separately and asked to participate in their respective surveys evaluating the effectiveness of risk minimisation measures. The survey will be conducted via telephone interviews in the local languages for parents/carers and for referring HCPs. Parent/Carers and referring HCPs survey are distinct and results will not be linked for confidentiality reasons.

In order to be considered eligible to participate in the study, HCPs will be required to meet the following criteria:

- HCPs or HCPs' close family members may not have been employees of GlaxoSmithKline, Pharmaceutical Product Development, LLC (PPD), the Food and Drug Administration (FDA), or the European Medicines Agency (EMA).
- HCPs must be licensed.
- An HCP must not have previously completed a survey regarding Strimvelis educational materials.
- An HCP must have previously referred a patient for Strimvelis treatment.

In order to be considered eligible to participate in the Parent/Carer survey, parents or carers will be required to meet the following criteria:

 Parents/carers or parents'/carers' close family members may not have been employees of GlaxoSmithKline, Pharmaceutical Product Development, LLC (PPD), the Food and Drug Administration (FDA), or the European Medicines Agency (EMA).

- A parent/carer must not have previously completed a survey regarding Strimvelis educational materials
- A parent's or carer's child must have previously received treatment with Strimvelis.

The study will recruit for approximately two years until 10 referring HCPs and 10 parents/carers have completed their respective surveys (length of study may vary contingent upon product uptake).

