8.3. Survey design

8.3.1. Survey Instruments

There are two survey instruments included in this study, (1) a HCP survey and (2) a parent/carer survey.

Following agreement to participate, the understanding of the potential risks associated with Strimvelis will be evaluated via telephone interview. The telephone interviews will be conducted in the local countries language. The survey will start with screening questions to ensure eligibility and willingness to participate in the survey. Participation in the study can be terminated during screening. The survey will include multiple choice and close-ended questions. There will be no open-ended questions included.

Survey questions are based on the Strimvelis prescribing information and educational materials including those that address risks of autoimmunity, unsuccessful response, oncogenesis and pregnancy. There will be approximately 20 questions per survey.

For HCPs, the survey refers to the following risk minimisation measures:

- Educational materials:
 - Important risk minimisation information for healthcare professionals who provide long-term follow-up of ADA-SCID patients post-treatment with Strimvelis
- Strimvelis Summary of Product Characteristics

For parents/carers, the survey refers to the following risk minimisation measures:

- Educational materials:
 - "Important follow-up risk minimisation information for children who have received gene therapy with Strimvelis (autologous CD34+ cells transduced to express ADA) an educational leaflet for parents/carers"
 - Patient Treatment Alert Card
- Strimvelis Patient Information Leaflet

The questions will evaluate HCPs' and patients'/carers' understanding of the key risk messages (KRMs) of the routine and additional risk minimisation measures. The questions will also assess HCPs' and patients'/carers' awareness, receipt, and reading of the educational materials. Demographic information such as geographic region and HCP specialty will also be captured (see Annexes 4 and 5). This information is required to further characterise the respondent population, including the number of patients.

The KRM topics for both the HCP and parent/carer surveys are listed in Section 8.3.3:

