8.3.3. Outcome definitions

This study will assess the proportion of parents/carers and referring HCPs at six months post treatment with Strimvelis that understood the possible risks relating to:

Safety concerns (KRM topics):

- 1. Malignancy due to insertional oncogenesis (e.g. leukaemia, myelodysplasia)
- 2. Autoimmunity
- 3. Unsuccessful response to gene therapy
- 4. Pregnancy

Other areas of interest:

- Requirement for long-term monitoring
- Receipt of the patient treatment alert card

The proportion of parents/carers and referring HCPs who acknowledge receipt of routine and additional risk minimization measures (e.g., SmPC/PIL, educational materials, Patient Alert Card) will be assessed as a measure of implementation.

The type of medical specialty and experience of referring HCPs will be summarized.

The primary outcome of these surveys is the proportion of parents/caregivers and referring HCPs that provide correct responses to a series of questions concerning the specific risks associated with Strimvelis.

Sufficient understanding of a key risk message can be assumed if at least 80% or more respondents correctly answer all questions that are included within that particular key risk message [ISPE White Paper 2016].

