8.5. Study size

All parents/carers and referring HCPs from patients enrolled in the Strimvelis product registry will be invited to complete the surveys. The study will recruit for approximately two years until 10 referring HCPs and 10 parents/carers have completed their respective surveys (length of study may vary contingent upon product uptake).

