9.1. Ethical approval and subject consent

The survey participation is voluntary.

Parents/carers being followed within the long-term registry, who have specifically agreed to be contacted for such studies, will be asked to consider and give informed consent for this study of their understanding of educational materials.

HCPs involved in the long term registry will also be asked to provide informed consent for their participation in this survey.

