16. ANNEX 4: HEALTHCARE PROVIDER SURVEY

The purpose of this survey is to assess your understanding of the risks associated with Strimvelis gene therapy.

SCREENING QUESTIONS	Yes	No	I don't know
Are you or any of your close family members an employee of GlaxoSmithKline, Pharmaceutical Product Development, LLC (PPD), the Food and Drug Administration (FDA), or the European Medicines Agency (EMA)?	[Terminate]		[Terminate]
This survey is voluntary. Do you agree to take part in this survey?		[Terminate]	[Terminate]
We appreciate your participation, no payment for completion of the survey can be provided. Do you wish to continue with the survey?		[Terminate]	[Terminate]
Have you previously taken part in a survey of your knowledge of educational materials about Strimvelis?	[Terminate]		
Are you a licensed medical healthcare provider?		[Terminate]	[Terminate]
Have you previously referred one of your patients to an Italian Strimvelis treatment centre?		[Terminate]	[Terminate]

DEMOGRAPHY QUESTIONS:

-
Demography Q1: How many patients have you referred to for treatment with Strimvelis?
Demography Q2: How would you classify your primary medical speciality?
Please select one response.
a. Paediatrician
b. Immunologist
c. Haematologist
d. Other (please specify):
Demography Q3: In what country is your primary medical practice?
Demography Q4: What is the length of your experience in your primary medical speciality?

WWEpi Project number: PRJ2678/205881

- a. Less than 3 years
- b. More than 3 and up to 5 years
- c. More than 5 and up to 10 years
- d. More than 10 and up to 15 years
- e. More than 15 years
- f. Prefer not to answer

Demography Q5: How many patients with ADA-SCID are you currently treating?

<#>

MAIN SURVEY QUESTIONS:

1. Have you received copies of the following educational materials about Strimvelis for healthcare providers?

Select all that apply.

- a. Important risk minimization information for healthcare professionals who provide long-term follow-up of ADA-SCID patients post-treatment with Strimvelis.
- b. Summary of Product Characteristics (SmPC).

If you answered "No" to all of the above materials, prior to this survey, were you aware of these educational materials about Strimvelis?

Please select one response.

- a. Yes
- b. No
- c. I don't know (I cannot remember)
- 2. Did you read the provided educational materials about Strimvelis?

Please select one response.

a. Yes
b. No
c. Some
d. I don't know
If Some, which ones did you read?

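### HCPs qualify by a past referral, but two scored malignancy items (Q10, Q11) ask what they did for the patient and no item records a follow-up role, so three non-following referrers could by themselves put KRM 1 below 80%.

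*Protocol*

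**What the plan says.** **Who is surveyed.** Protocol 8.2 sets the link to the patient as "An HCP must have previously referred a patient for Strimvelis treatment". The Annex 4 screener applies it by asking "Have you previously referred one of your patients to an Italian Strimvelis treatment centre". Neither requires a role after treatment.

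**What the HCPs are given.** Section 8.3.1 names one HCP educational document, "Important risk minimisation information for healthcare professionals who provide long-term follow-up of ADA-SCID patients post-treatment with Strimvelis", together with the SmPC. Section 6.2 says who receives the materials: "These additional risk minimization measures, including educational materials, will be distributed to parents/carers and referring HCPs".

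**What is scored.** In Annex 4, Q9 to Q11 carry the KRM 1 tag. Q9 is a true/false item on a contraindication. Q10 and Q11 are yes/no items on what the respondent has done: advice on signs of leukaemia, and blood tests in the first year after the patient's return. Table 4 in Annex 2 puts Q6 to Q11 in the malignancy block under a heading for correct answers. The two places draw the block differently, but Q10 and Q11 are in both.

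**The rule.** Section 8.3.3 takes a message as understood if "at least 80% or more respondents correctly answer all questions that are included within that particular key risk message". Section 8.5 recruits until "10 referring HCPs and 10 parents/carers have completed their respective surveys".

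**What is recorded about the respondent.** Demography Q1 to Q5 cover patients referred, specialty, country, years of experience and ADA-SCID patients currently treated. The Annex 4 text at hand stops after Q13, but Tables 3 to 5 list the whole HCP survey and hold no question on post-Strimvelis follow-up.

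**The concern.** KRM 1 is meant to measure understanding of malignancy risk. Q10 and Q11 measure practice, and practice depends on whether the respondent sees the patient after treatment. A referrer whose patient is followed elsewhere may know the malignancy message fully and still have no blood tests to report. Under the all-items rule, that one truthful 'No' makes the respondent a KRM 1 failure.

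At stake is how a KRM 1 shortfall is read. It could mean that the leaflet or SmPC did not convey the risk, or that some respondents had no follow-up role. The first would call the risk minimisation measures into question; the second would not. The planned data cannot tell them apart. Nor can the role be recovered later: 8.2 rules out linking the HCP and parent/carer surveys, and 8.6.3 plans no further contact.

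**Working it through.** The protocol gives no derivation for 10 HCPs and calls the study descriptive, so there is no sample-size figure to reproduce. The check takes the 80% rule at n = 10 and varies the number of non-following respondents.

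**Inputs from the protocol**
- n = 10 completed HCP surveys (8.5)
- threshold 80%, all items of the message correct (8.3.3)
- Q10 and Q11 scored in the malignancy block (Annex 2 Table 4; Annex 4)

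**Assumptions**
- 'Yes' is the answer keyed as correct for Q11; the protocol text shows no key.
- A non-following referrer answers Q11 'No'. Q10 is less certain, because advice can be given without being the follow-up doctor, so the calculation rests on Q11 alone.
- The share of non-following referrers is not given; a range of 10% to 40% is used.

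**Step 1: threshold.** 0.80 × 10 = 8 respondents must pass, so at most 2 may fail.

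**Step 2: ceiling on KRM 1.** With k non-followers, the best possible result is (10 − k)/10:
- k = 0, 1, 2: 100%, 90%, 80%; the threshold can be met
- k = 3: 7/10 = 70%; it cannot be met

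**Step 3: chance of passing when all followers are perfect.** KRM 1 passes if at most 2 of 10 are non-followers. With share f, P = (1−f)^10 + 10·f·(1−f)^9 + 45·f²·(1−f)^8.
- f = 0.20: 0.107 + 0.268 + 0.302 = 0.68
- f = 0.30: 0.028 + 0.121 + 0.233 = 0.38
- The complement, three or more non-followers, is 0.07, 0.32, 0.62 and 0.83 at f = 0.10, 0.20, 0.30 and 0.40.

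**Step 4: followers not perfect.** If each follower passes KRM 1 with probability p (assumed), P(pass) = P(Bin(10 − k, p) ≥ 8):

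| Non-followers k | p = 0.95 | p = 0.90 |
|---|---|---|
| 0 | 0.99 | 0.93 |
| 1 | 0.93 | 0.78 |
| 2 | 0.66 | 0.43 |
| 3 | 0 | 0 |

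One or two non-followers already lower the chance of passing markedly.

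**Step 5: KRM 2 and KRM 3.** Q12 to Q18 ask what is known or recommended, and a non-follower can answer them. If followers pass with probability 0.90 and non-followers with 0.50 to 0.70 (both assumed), three non-followers lower P(pass) from 0.93 to between 0.62 and 0.80. With equal knowledge there is no effect.

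**Step 6: what recording the role would show.** Three non-followers and seven perfect followers read 7/10 = 70% combined, but 7/7 = 100% among those who follow patients.

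**The case against.** The strongest reply is that the plan surveys the people it means to survey. Sections 7, 8.1, 8.2, 8.3.3 and 8.5 all name referring HCPs, and 6.2 sends them the materials. The survey also covers the SmPC, which is not confined to follow-up doctors. A referrer who was sent the material and cannot answer a knowledge item is a genuine result. No passage shows that any referrer lacks a follow-up role, and Q11's wording, about a patient coming back from treatment, suggests that patients return to the respondent. The study is descriptive, 8.7.1 reports each question separately, and Demography Q5 gives a partial proxy.

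Most of this stands, and it rules out three stronger readings.
- A reader might infer that the protocol mixes three HCP populations: referrers, the leaflet's addressees, and those in 9.1 ("HCPs involved in the long term registry will also be asked to provide informed consent for their participation in this survey"). The 9.1 phrase reads naturally as the referring HCPs of registry patients. It is loose wording, not a rival population.
- A reader might take the background as evidence that referrers hand patients on. The sentence in 6.1 ("before care is eventually transferred to a pediatric immunologist, who may ultimately make the diagnosis and consider treatment options") describes movement up to diagnosis and treatment choice, not after Strimvelis.
- A reader might extend the 70% cap to KRM 2 and 3. That would need non-followers to fail knowledge items with certainty, which nothing supports.

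The reply does not reach Q10 and Q11. Per-question tables will show how many answered 'No' but not why. Demography Q5 counts ADA-SCID patients under treatment, with or without Strimvelis, and is not tied to the referred patient. Q11 cannot serve as the role marker because it is itself a scored item.

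**Conclusion.** The point holds for KRM 1. Eligibility by referral, scoring of what the respondent has done, and the lack of any record of follow-up role together mean that a KRM 1 shortfall among HCPs could not be interpreted. Three of 10 respondents suffice to cause it. That threshold follows from the protocol's own numbers, given that 'Yes' is the keyed answer to Q11 and that non-followers answer 'No'. How likely it is rests wholly on the assumed share of non-followers; if nearly all referrers follow their patients, the effect is small, but the survey as designed could not show that.

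Surveying referring HCPs is legitimate, and the documents do not show that the wrong people are surveyed or that referrers fail to receive the materials. For KRM 2 and 3 the effect is conditional and weaker. This is a cheap improvement in interpretability, not a flaw that invalidates the HCP survey.

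**What to change.** 1. Add one closed item to the Annex 4 demography block, and to Tables 3 and 5: 'Do you provide post-treatment follow-up for a patient treated with Strimvelis? Yes/No'.
2. In 8.7.1 and Table 4, report the HCP KRM results, KRM 1 above all, by this item beside the combined figure. The combined figure for all referring HCPs stays the main result, since that is the population in the objective.
3. State in 8.3.3 or 8.7.1 that a 'No' to Q10 or Q11 from an HCP without a follow-up role is not read as lack of understanding.

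The cost is one extra question in a survey of about 20, extra columns in Table 4 and a sentence of text. The subgroup figures will be imprecise: with seven followers, one respondent moves the result by 1/7, about 14 percentage points, against 10 points in the full group. They should be presented as context for the combined result. The item will not bring in follow-up doctors who did not refer; it only shows which respondents have the role.
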